2.6.2 Evaluation of ADA on Relevant Safety Parameters

To evaluate the effect of ADA and NAb on AEs, the number and percentage of patients experiencing any TEAEs, any treatment-emergent SAEs, or any IARs, hypersensitivity (narrow SMQ), and anaphylaxis (narrow SMQ) will be presented by the following sub-categories: 1. ADA status (ever positive, always negative) 2. ADA peak titer category (always negative, peak titer

100-800, 1600-6400, $\geq 12,800$) 3. ADA response type (always negative, transient response (if occur), and persistent responses subcategories: low response, intermediate response, high ADA response and tolerized at defined timepoints. 4. Correlation of frequency of IAR and ADA peak titer. 5. Neutralizing antibody status (always negative, ever positive). Pertinent groups will be assessed to address both treatment naïve and switch patients.

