- The ADA attributes will be determined by the following conditions (note that some cases may not be applicable to the current study due to the treatment naïve study population):
- Pre-existing ADAs: antibodies reactive with the study drug present in subjects before treatment. The week 49 timepoint will provide data on pre-existing ADAs to avalglucosidase alfa in the alglucosidase alfa treatment arm.
- Treatment induced ADAs: ADAs developed de novo (seroconversion) following administration of the study drug. If the baseline ADA sample is missing or non-reportable and at least one reportable on-treatment ADA sample is available, the baseline sample will be considered as “negative”.

- Treatment boosted ADAs: Pre-existing ADAs that were boosted at least two titer steps from baseline (ie, 4 fold increase in titers) following administration of the study drug (any time after the first drug administration).

The following kinetics of the ADAs will be analyzed:

- Onset of ADA is defined as the time period (in days) between the first study drug administration and the first instance of treatment induced ADAs.
- Duration of ADA will be calculated as the date of last treatment induced ADA sample minus date of first treatment induced ADA sample + 1.

The following ADA response classifications will be used:

1. Treatment-induced ADA- patients are ADA negative at baseline and have developed an ADA response
 - a. Transient ADA response is defined as: 1) Treatment-induced ADA detected only at one sampling timepoint post-baseline (excluding the last sampling time point); or 2) Treatment-induced ADA detected at two or more sampling time points post-baseline, where the first and the last ADA-positive samples (irrespective of any negative samples in between) are separated by a period of less than 16 weeks, and the subject's last sampling time point is ADA-negative
 - b. Persistent ADA response is defined as: 1) Treatment-induced ADA detected at two or more sampling time points post-baseline, where the first and the last ADA-positive on-treatment sample (irrespective of any negative samples in between) are separated by at least 16 weeks; or 2) Treatment-induced ADA detected in the last two sampling time points, irrespective of the time period in between.

The following subclassifications for persistent ADA response will be considered as well. The titer values are based on LOTS alglucosidase alfa clinical experience.

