2.6 ANALYSES OF SAFETY DATA

In PAP analysis, the safety analyses will be carried out with patients by the actual treatment received, irrespective of the treatment the patient has been randomized to.

- In ETP analysis and overall evaluation of avalglucosidase alfa safety, the safety analyses will be carried out by the following 4 groups:
- Group 1 includes data in PAP and ETP among subjects who received avalglucosidase alfa in PAP and ETP,
- Group 2 includes data in ETP among subjects who received alglucosidase alfa in PAP and received avalglucosidase alfa in ETP,
- Group 3 includes data in PAP and/or EPT among subjects who received avalglucosidase alfa in that period,

- Group 4 includes data in PAP and/or EPT among pediatric subjects who received avalglucosidase alfa in that period.

General rules

All safety analyses will be performed on the safety population as defined in [Section 2.3.2](#), unless otherwise specified, using the following common rules:

- The baseline value is the last available value before the start of first infusion in PAP or ETP, except possibly ECG parameters. The complete definitions of baseline are listed in [Section 2.1.1](#).
- The potentially clinically significant abnormality (PCSA) values are defined as abnormal values considered medically important by the Sponsor according to predefined criteria/thresholds based on literature review and defined by the Sponsor for clinical laboratory tests, vital signs, and ECG (PCSA version dated May 2014 [[Appendix A](#)]).
 - PCSA criteria will determine which patients had at least 1 PCSA during the treatment epoch, taking into account all evaluations performed during the period, including nonscheduled or repeated evaluations.
 - The number of all such patients will be the numerator for the on-treatment PCSA percentage; the denominator will be the number of patients assessed for that given parameter in the treatment epoch in the safety population.
- The analysis of the safety variables will be essentially descriptive and no inferential testing is planned.

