2.6.9 Association of ADA with PK

The following analysis will be considered: 1. Within Subject level AUC change from baseline to end of the double-blind treatment period will be plotted by peak titer category. Gender will be separated by different color. 2. Between subject comparison of ADA-positive vs. ADA negative. Plot of AUC at baseline compared to timepoints where full PK assessment is available. Patients will be evaluated by titer categories based on titer category at the time of PK assessment. Patients will be separated based on treatment groups. 3. Summary table to include AUC and % change from Day 1 at each scheduled visit by peak titer categories. 4. Data will be assessed for switch patients as appropriate.

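### SAP 2.6.2 relates adverse events to whole-period antibody labels without regard to event order or exposure, so tables combining PAP and ETP can show an association produced by follow-up time alone

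*SAP*

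**What the plan says.** SAP 2.6.2 states its purpose as "To evaluate the effect of ADA and NAb on AEs". The outcome is "the number and percentage of patients experiencing any TEAEs, any treatment-emergent SAEs, or any IARs, hypersensitivity (narrow SMQ), and anaphylaxis (narrow SMQ". Patients are grouped by "ADA status (ever positive, always negative", by peak titer category, then by response type and by whether neutralizing antibody was ever positive. A further item is "Correlation of frequency of IAR and ADA peak titer". The section says that relevant groups will cover naive and switch patients, but does not name the groups or the periods.

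SAP 2.6 defines the groups for ETP and overall safety. Group 1 combines PAP and ETP data for patients on avalglucosidase alfa in both. Group 2 holds switch patients in ETP. The third is broader: "Group 3 includes data in PAP and/or EPT among subjects who received avalglucosidase alfa in that period". The same section calls the safety analyses essentially descriptive, with no inferential testing.

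The pieces of a time-based analysis are already planned elsewhere:

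- SAP 2.1.4.8 derives antibody onset for each patient: "Onset of ADA is defined as the time period (in days) between the first study drug administration and the first instance of treatment induced ADAs". It also sets ADA sampling at Week 2, monthly through PAP and the first 6 months of open-label treatment, and every 3 months after that.
- SAP 2.6.1 plans exposure-adjusted incidence rates for the adverse event overview and by SOC and PT, but not by ADA category. It also tabulates IARs by start time relative to infusion.
- SAP 2.6.9 says for one PK comparison: "Patients will be evaluated by titer categories based on titer category at the time of PK assessment".

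**The concern.** Two features of 2.6.2 deserve separate treatment.

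**Order.** A patient who reacts at the first infusion and seroconverts two months later is counted as an antibody-positive patient with a reaction. The table cannot tell that sequence from its reverse, yet the stated purpose is an effect of antibody on events.

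**Exposure.** Ever having a positive sample, reaching a high peak titer and ever having an IAR all become more likely with longer observation. Where follow-up differs between patients, the long-followed collect in the cell with both and the short-followed in the cell with neither. That is an association even if antibody and reaction are unrelated.

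IARs are an adverse event of special interest (Protocol 10.4.1.3), and the development of ADA is among the safety data that the 12-month period is meant to capture (Protocol 6.5). A reader of the study report will want this table to say whether antibodies precede reactions.

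**Working it through.** **Inputs.** The plan states no figure to reproduce, and the documents give no ADA or IAR rates. From the documents:

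- Follow-up: PAP lasts 49 weeks and the extension up to 96 and then up to 144 more weeks (SAP 1.1), so at most 49 + 96 + 144 = 289 weeks. The last phase ends earlier on local approval.
- Dropout: 10% is assumed; in the placebo-controlled alglucosidase alfa trial, 57 of 60 treated patients had evaluable data at Month 12 (SAP 1.3.3).

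Assumed: constant, independent hazards of ADA, a = 0.01 to 0.03 per week, and of first IAR, b = 0.003 to 0.006 per week. There is no true link.

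**Formula.** For follow-up F uniform on (L, U), let M(x) = E[exp(−xF)] = (exp(−xL) − exp(−xU)) / (x(U − L)). The four cells are:

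- always negative, no IAR: M(a+b)
- always negative, IAR: M(a) − M(a+b)
- ever positive, no IAR: M(b) − M(a+b)
- ever positive, IAR: 1 − M(a) − M(b) + M(a+b)

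**Worked case.** Take a = 0.01, b = 0.003 and 49 to 200 weeks.

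- M(a) = (0.6126 − 0.1353)/1.51 = 0.3161
- M(b) = (0.8633 − 0.5488)/0.453 = 0.6942
- M(a+b) = (0.5289 − 0.0743)/1.963 = 0.2316
- Cells, in the order above: 0.2316, 0.0845, 0.4626, 0.2213
- Odds ratio = (0.2213 × 0.2316)/(0.4626 × 0.0845) = 1.31

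**All corners of the assumed hazards.**

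| Follow-up | Null odds ratio |
|---|---|
| 49 weeks, equal | 1.00 |
| 49 weeks, 10% leaving uniformly before | 1.06 to 1.15 |
| 49 to 97 weeks | 1.06 to 1.12 |
| 49 to 200 weeks | 1.31 to 1.78 |

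The false association therefore comes from the spread of follow-up. Ignoring order, with equal and uninformative follow-up, gives exactly 1.

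**What ignoring order does.** Among patients with both ADA and an IAR by F = 49 weeks, the share whose first IAR came before the antibody is [(1 − e^(−aF)) − (a/(a+b))(1 − e^(−(a+b)F))] / [(1 − e^(−aF))(1 − e^(−bF))]. For a = 0.03 and b = 0.003 this is (0.7701 − 0.7286)/(0.7701 × 0.1367) = 39%. Over the assumed hazards it is 39% to 48%. With median seroconversion of 8 weeks (a = ln 2/8) it is 23% to 24%.

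**Check with the planned sampling schedule.** A separate null simulation assumed 25% or 40% of patients with an IAR by 48 weeks, between-patient variation in IAR risk, and median seroconversion of 8 or 24 weeks. It pooled naive patients (48 to 144 weeks) with switch patients (1 to 96 weeks).

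- At the 25% rate, an IAR occurred in 33% to 35% of ever-positive and 8% to 26% of always-negative patients.
- Over both rates, IAR count and peak titer had a mean rank correlation of +0.13 to +0.22.
- If instead 30% of patients stopped after an IAR (PAP only, 25% rate), the table reversed: 22% to 23% against 27% to 50%. The bias can run either way.
- At the 25% rate, person-time after against before the first positive sample, in 4-week strata since first infusion, gave rate ratios of 0.99 to 1.02 in every scenario.

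**The case against.** The strongest defence has four parts.

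- **PAP is the main safety period, with nearly equal follow-up.** This stands. A reader might infer that ignoring event order by itself manufactures an association, or that the PAP tables are seriously biased. The calculation supports neither.
- **The pooling is inferred.** SAP 2.6.2 does not name Group 3, and SAP 2.6.8.3 and 2.6.8.4 handle naive and switch patients separately. This stands in part: separate tables would reduce the problem, but follow-up within Group 1 would still vary.
- **Order can be traced case by case.** Hypersensitivity and anaphylaxis cases get listings and medical review (SAP 2.6.1), and antibody data are listed by patient (Protocol 11.4.4.4). True, but no summary does this. SAP 1.6 also mentions an integrated immunogenicity analysis plan, which is not available here and may cover timing. If it does, 2.6.2 should say so.
- **The contrast with PK is partial.** SAP 2.6.9 uses titer at the time of assessment for one item and peak titer for others. So 2.6.2 does not break a uniform rule of the SAP; the time-matched method is merely already in use there.

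A much larger distortion is also tempting. Follow-up uniform on 4 to 200 weeks gives odds ratios of 1.9 to 3.9, but it has (49 − 4)/(200 − 4) = 23% of patients leaving before Week 49, against the 10% that the SAP assumes. The documents do not support that range.

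**Conclusion.** The concern holds, mainly for tables that combine PAP and ETP. With no true link, their odds ratio would be about 1.1 for follow-up of 49 to 97 weeks and about 1.3 to 1.8 for 49 to 200 weeks. In PAP alone it would be about 1.0 to 1.15. There the fault is misattribution: a sizeable share of reactions in antibody-positive patients may precede the antibody, which can blur a real effect.

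These sizes rest on assumed hazards and an assumed spread of follow-up. They also shift with the speed of seroconversion. At a = 0.03 and 49 to 200 weeks, only 5% of patients are always negative, about 5 of 96, so the observed ratio would be very imprecise. With faster seroconversion there is almost no comparator, and the peak-titer analyses carry the weight.

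A reader might infer that labelling or the trial's main result is at risk. The documents do not say that this table supports labelling. It is descriptive, and the primary efficacy conclusion does not depend on it.

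**What to change.** In SAP 2.6.2, add a supportive summary for IARs, hypersensitivity and anaphylaxis:

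- Assign each event the ADA and neutralizing status and the titer category of the last scheduled sample at or before it. Flag samples triggered by an IAR, which the protocol flow chart allows.
- Report events per 100 patient-years, or per 100 infusions, of time in each current category.
- Stratify by time since first infusion of the product concerned. Reactions may cluster early: with a threefold higher early IAR hazard, an unstratified null rate ratio came out at about 0.5.
- Show naive and switch patients separately, and name the groups and periods.

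Dividing by patient-years while keeping the ever-positive label is not enough: where 30% stopped after an IAR, that null rate ratio was 0.23 to 0.74.

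Keep the ever/always and peak-titer tables as descriptive, for PAP only, with IARs before and after the first positive sample side by side. Do not count only post-positive IARs in ADA-positive patients while counting all IARs in always-negative ones; that adds immortal-time bias. With IARs recurring at constant rate b over F = 49 weeks, the ever-positive proportion becomes 1 − [a e^(−bF)(1 − e^(−(a−b)F))/(a − b)]/(1 − e^(−aF)). For a = 0.03 and b = 0.006 that is 16.3%, against 1 − e^(−bF) = 25.5%, a null odds ratio of 0.57. The range is 0.49 to 0.60 over the assumed hazards, and about 0.75 at 8-week median seroconversion.

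The cost is SAP wording and one derived dataset, with no new samples. Cells will be sparse, and ADA status between samples remains uncertain, more so once sampling is quarterly.

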2.6.3 Deaths

The following summaries of deaths will be generated for the safety population.

- Number (%) of patients who die by study period (on-study, PAP treatment epoch, ETP treatment epoch, post treatment epoch) and reasons for death,
- Deaths in nonrandomized patients or randomized but not treated patients,
- Treatment-emergent adverse events leading to death (death as an outcome on the adverse event case report form page as reported by the Investigator) by primary SOC, and PT. Corresponding listing will be provided as well.

2.6.4 Analyses of laboratory variables

The summary statistics (including number, mean, median, SD, minimum and maximum) of all laboratory variables (laboratory values and changes from baseline) will be calculated for each visit or study assessment (baseline and each postbaseline time point, by treatment group. This section will be organized by biological functions.

The number (%) of patients with laboratory abnormalities of all laboratory variables, when applicable, will be summarized for each visit or study assessment. Comparisons of the worst laboratory abnormalities during PAP with the baseline will be presented for each laboratory parameter, when applicable. Similar analyses will be conducted combining both PAP and ETP together, but only for the patients in avalglucosidase alfa group.

The incidence of PCSAs (list provided in [Appendix A](#)) at any time during the treatment-emergent adverse event period will be summarized by biological functions and treatment groups.

- The PCSA analyses will be conducted for PAP primarily. Similar analyses will be conducted combining both PAP and ETP together, but only for the patients in avalglucosidase alfa group.

Drug-induced liver injury

The liver function tests, namely AST, ALT, alkaline phosphatase, and total bilirubin, are used to assess possible drug-induced liver toxicity. The following analyses will be performed:

- Time to onset of the initial ALT or AST elevation ($>3 \times \text{ULN}$) and total bilirubin elevation ($>2 \times \text{ULN}$), whichever comes first will be analyzed using Kaplan Meier estimates by study cohort and treatment arm, if necessary.
- A graph of distribution of peak values of ALT versus peak values of total bilirubin (in logarithmic scale or in the scale of $x \text{ ULN}$ if appropriate) will also be presented. The graph

will be divided into 4 quadrants with a vertical line corresponding to 3 x ULN for ALT and a horizontal line corresponding to 2 x ULN for total bilirubin if necessary. A similar graph will be provided for peak values of AST versus peak values of total bilirubin.

- Listing of possible Hy's law cases identified by treatment group (eg, patients with any elevated ALT or AST >3 x ULN, and associated with an increase in bilirubin ≥ 2 x ULN) with ALT, AST, alkaline phosphatase and total bilirubin if necessary.
- Summary of the incidence of liver-related adverse events by treatment group if necessary. The selection of preferred terms will be based on the hepatic disorder SMQ.
- Additional similar analyses will be performed for the ETP and combined PAP and ETP period.

2.6.5 Analyses of vital sign variables

The summary statistics (including number, mean, median, SD, minimum and maximum) of all vital signs variables (central laboratory values and changes from baseline) will be calculated for each scheduled visit or study assessment (baseline, each postbaseline time point) by treatment group.

The incidence of PCSAs (list provided in [Appendix A](#)) based on worst value at any time during the treatment-emergent adverse event period will be summarized by treatment groups.

The PCSA analyses will be conducted for both PAP and ETP separately. Similar analyses will be conducted for combined PAP and ETP period.

2.6.6 Analyses of electrocardiogram variables

The summary statistics (including number, mean, median, SD, minimum and maximum) of all ECG variables (laboratory values and changes from baseline) will be calculated for each visit or study assessment (baseline, each postbaseline time point) by treatment group.

The incidence of PCSAs (list provided in [Appendix A](#)) based on worst value at any time during the treatment-emergent adverse event period will be summarized by treatment groups.

The PCSA analyses will be conducted for both PAP and ETP separately. Similar analyses will be conducted for combined PAP and ETP period.

2.6.7 Analyses of physical examinations

The summary statistics of all physical examination variables will be summarized descriptive by treatment group if appropriate.

2.6.8 Analyses of Immunogenicity parameters

2.6.8.1 ADA incidence and characterization

ADA status: ADA seroconversion is classified as always negative and ever positive. Baseline ADA status will be reported as negative or pre-existing ADA at initiation of treatment as well as at drug switch after PAP period.

The following ADA incidence will be summarized descriptively for each treatment group during the PAP and baseline will be reassessed at the beginning of ETP for the alglucosidase alfa treated patients that switch to avalglucosidase alfa.

- Treatment emergent ADA incidence, defined as
 - $100 \times (\text{treatment boosted} + \text{treatment induced ADA positive patients}) / (\text{number of evaluable patients})$,
- Treatment induced ADA incidence, defined as,
 - $100 \times (\text{treatment induced ADA positive patients}) / (\text{number of evaluable patients with ADA negative at baseline})$,
- Treatment boosted ADA incidence, defined as
 - $100 \times (\text{treatment boosted ADA positive patients}) / (\text{number of evaluable patients with ADA positive at baseline})$,

2.6.8.2 Duration of ADA

The kinetics and duration of the immune responses will be analyzed as follow:

- Onset time of ADA will be analyzed descriptively using summary statistics minimum, Q1, median, Q3 and maximum.
- Duration of ADA will be analyzed descriptively using summary statistics minimum, Q1, median, Q3 and maximum. It will only be calculated for the patients with at least two ADA positive samples. The median duration and the quartiles will be reported.

2.6.8.3 ADA titers

- ADA peak titer, last titer, and geometric mean titer will be summarized. Graphs of ADA titer over time and boxplots of the highest post-baseline ADA titer will be provided. The analyses will be performed for PAP, ETP and combined PAP and ETP periods. Both treatment naïve and switch patients will be evaluated separately.

2.6.8.4 ADA Response Classification

Response type classification will be provided separately for treatment naïve and switch patients as follows:

- The number and percent of transient ADA response will be summarized descriptively. This will be performed for the patients with at least two post baseline samples where the last sampling timepoint is negative.
- The number and percent of persistent ADA response and its subclassifications will be summarized descriptively. This will be performed for the patients with at least two post baseline samples which are separated by at least 16 weeks.
- The number and percent of indeterminate ADA response will be summarized descriptively. This will be performed for the patients with at least one post baseline sample.

2.6.8.5 Neutralizing ADA

- Incidence of neutralizing antibodies (inhibition of enzyme activity and inhibition of enzyme uptake) will be reported for both treatment naïve and switch patients
- Onset time of neutralizing ADA will be analyzed descriptively using summary statistics minimum, Q1, median, Q3 and maximum.
- Duration of neutralizing ADA will be analyzed descriptively using summary statistics minimum, Q1, median, Q3 and maximum. It will only be calculated for the patients with at least two neutralizing ADA positive samples.

2.6.8.6 Cross-reactivity evaluation

Cross reactivity will be assessed at Week 25 and Week 49 during the PAP. Patients from the avalglucosidase alfa treatment arm who are positive for anti-avalglucosidase alfa antibodies will be tested to determine if the antibodies cross-react with alglucosidase alfa and patients from the alglucosidase treatment arm who are positive for anti- alglucosidase alfa antibodies will be tested to determine if the antibodies cross-react with avalglucosidase alfa at these timepoints. ADA titer data for the cross-reactivity assessment will be analyzed descriptively by treatment group using summary statistics minimum, Q1, median, Q3 and maximum to both molecules. A patient listing of titers will also be provided. In addition, patients from the avalglucosidase alfa treatment arm who are positive for anti-avalglucosidase alfa antibodies will be further evaluated by immunodepletion to determine cross-reactivity. The percentage of patients with cross-reactive antibodies will be provided.

